^f A salivary 17-OHP profile should be collected by the subjects on Days -8, 22, 50, and 78. These samples should be obtained at approximately 8 AM (08:00), noon (12:00), 4 PM (16:00), 8 PM (20:00), and 10-11 PM (22:00-23:00). At Visits T1, T2, T3, and T4, saliva samples for 17-OHP will be collected at the study site at approximately 8 AM (08:00), 10 AM (10:00), and noon (12:00). The 8 AM (8:00) sample should be collected prior to the subjects' morning dose of GC and MC (if applicable) and will also be assessed for P (in premenopausal women only) and cortisol. The timing of the 8 AM (08:00), 10 AM (10:00) (if applicable), and noon (12:00) samples should be adjusted to correspond to just before, 2 hours after, and 4 hours after (respectively) administration of the morning replacement glucocorticoid, mineralocorticoid (if applicable) and/or study drug (if applicable) doses.

^g On the days marked, a pregnancy test will be done on female subjects of childbearing potential only. A serum pregnancy test will be done at Screening; a urine pregnancy test will be done at Visit S2 (if applicable), B1, T1, T2, T3, T4/EoT, and F1/EoS. The start date of the subject's last menstrual period will be obtained for premenopausal women only.

^h Subjects will use the eDiary to record their glucocorticoid and mineralocorticoid (if applicable) doses (and, for premenopausal women, start dates of menstrual periods) from B1 to F1, and will also record their study drug doses from T1 to T4. The eDiary may also be used to provide reminders to subjects.

ⁱ Subjects with a 17-OHP level from Visit S1 < 4x ULN (Cohort 2) and a daily maintenance GC dose \geq the equivalent of 12 mg hydrocortisone/m² body surface area will be contacted approximately 2 weeks after Visit S1 to have their GC dose decreased by the equivalent of approximately 5 mg hydrocortisone or 1 mg prednisone or prednisolone. They will then return for Visit S2 at least 2 weeks later. If their 17-OHP level from Visit S2 is \geq 4x ULN, they will enter the Baseline period; if not, the case should be discussed with the Medical Monitor.

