- ^e For each study visit, the first blood and saliva hormone sample should be collected in the morning prior to the subjects' morning dose of GC and MC (if applicable) replacement, as close to 8 AM (08:00) as practicable and between the hours of 6-10 AM (06:00-10:00). For Cohort 2 subjects who undergo GC dose adjustment, results from the serum 17-OHP samples obtained during Screening and Baseline will be used to assess stability of 17-OHP. Cohort 2 subjects who undergo GC dose adjustment, whose subsequent serum 17-OHP results during Screening and Baseline do not indicate stable levels, should be discussed with the Medical Monitor (see Appendix 2). At Visits T1, T2, T3, T4, and T5/EoT, blood sample collections for 17-OHP will also occur approximately 1, 2, 3, and 4 hours after administration of the morning replacement glucocorticoid, mineralocorticoid (if applicable) and/or study drug (if applicable) doses.
- ^f A salivary 17-OHP profile should be collected by the subjects on Days -8, 22, 50, 78, and 106. These samples should be obtained at approximately 8 AM (08:00), noon (12:00), 4 PM (16:00), 8 PM (20:00), and 10-11 PM (22:00-23:00). At Visits T1, T2, T3, T4, and T5, saliva samples for 17-OHP will be collected at the study site at approximately 8 AM (08:00), 10 AM (10:00), and noon (12:00). The 8 AM (8:00) sample should be collected prior to the subjects' morning dose of GC and MC (if applicable) and will also be assessed for P (in premenopausal women only) and cortisol. The timing of the 8 AM (08:00), 10 AM (10:00) (if applicable), and noon (12:00) samples should be adjusted to correspond to just before, 2 hours after, and 4 hours after (respectively) administration of the morning replacement glucocorticoid, mineralocorticoid (if applicable) and/or study drug (if applicable) doses.
- ^g On the days marked, a pregnancy test will be done on female subjects of childbearing potential only. A serum pregnancy test will be done at Screening; a urine pregnancy test will be done at Visit S2 (if applicable), B1, T1, T2, T3, T4, T5/EoT, and F1/EoS. The start date of the subject's last menstrual period will be obtained for premenopausal women only.
- ^h Subjects will use the eDiary to record their glucocorticoid and mineralocorticoid (if applicable) doses (and, for premenopausal women, start dates of menstrual periods) from B1 to F1, and will also record their study drug doses from T1 to T5. The eDiary may also be used to provide reminders to subjects.

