3.2 Coding Systems and Conventions

3.2.1 Definition of Baseline

In general, all values recorded at Visit T1 (Day 1) prior to the first dose will be regarded as baseline values for this study. In case no predose Visit T1 (Day 1) value was recorded (expected for ECG and for coagulation parameters), the most recent value prior to Visit T1 (Day 1) will be used as baseline value instead.

For serum or plasma 17-OHP, P, cortisol, A4, ACTH, total T, and 11-ketoT, baseline is defined as the mean of the predose value from Visit T1 (Day 1) and the most recent “0-hour” value prior to Visit T1 (Day 1), if the glucocorticoid dose was the same as at Visit T1 (Day 1) (if not the same, then only the predose Visit T1 (Day 1) value will be used).

For on-site salivary 17-OHP, P, and cortisol, baseline is defined as the mean of the predose value from Visit T1 (Day 1) and the most recent “0-hour” value prior to Visit T1, if the glucocorticoid dose was the same as at Visit T1 (if not the same, then only the predose Visit T1 value will be used). Change from baseline will be calculated for salivary 17-OHP values obtained 30 minutes before, as well as 2 hours and 4 hours after intake of the morning dose of nevanimibe HCl. For additional analyses, baseline for on-site salivary 17-OHP is further categorized by the time of sample relative to the time of the morning dose of nevanimibe HCl. Thus, baseline for the predose measurement on visits T2/T3/T4/T5 is defined for the additional analyses as above, while it is defined as the T1 sample taken 2 hours after the morning dose of nevanimibe HCl for the T2/T3/T4/T5 sample taken 2 hours after the morning dose, and defined as the T1 sample taken 4 hours after the morning dose for the T2/T3/T4/T5 sample taken 4 hours after the morning dose.

For home collection salivary 17-OHP profiles, baseline for the 8 AM (08:00), noon (12:00), 4 PM (16:00), 8 PM (20:00), and 10-11 PM (22:00-23:00) time points is defined as the value obtained for the corresponding time point at Day -8.

Except for the above-mentioned case, all values recorded after the first treatment with the study drug will be regarded as post-baseline values.

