6.3 Secondary Efficacy Endpoints

The following are secondary efficacy endpoints:

-Androstenedione, progesterone, total testosterone, and 11-ketotestosterone levels as measured at Baseline, Visit T2 (Day 29), Visit T3 (Day 57), Visit T4 (Day 85), Visit T5 (Day 113; Amendment 2) and Follow-up Visit (Day 113 (Amendment 1) or Day 141 (Amendment 2)); and change from Baseline to Visit T2 (Day 29), Visit T3 (Day 57), Visit T4 (Day 85), Visit T5 (Day 113; Amendment 2) and Follow-up Visit (Day 113 (Amendment 1) or Day 141 (Amendment 2)).

-Serum 17-OHP levels as measured at Visit T1 (Day 1), Visit T2 (Day 29), Visit T3 (Day 57), Visit T4 (Day 85), and Visit T5 (Day 113; Amendment 2) at h0, h1, h2, h3 and h4 (predose and 1-4 hours after administration of the morning replacement glucocorticoid, mineralocorticoid (if applicable), and/or study drug (if applicable) doses); and change from baseline (Visit T1 (Day 1)) to Visit T2 (Day 29), Visit T3 (Day 57), Visit T4 (Day 85), Visit T5 (Day 113; Amendment 2).

-Salivary 17-OHP levels as measured at Visit T1 (Day 1), Visit T2 (Day 29), Visit T3 (Day 57), Visit T4 (Day 85), and Visit T5 (Day 113; Amendment 2) (at time points h0, h2 and h4 (just before, 2 hours after, and 4 hours after (respectively) administration of the morning replacement glucocorticoid (if applicable), mineralocorticoid (if applicable) and/or study drug (if applicable) doses)) and change from Baseline (Visit T1 (Day 1)) to Visit T2 (Day 29), Visit T3 (Day 57), Visit T4 (Day 85), and Visit T5 (Day 113; Amendment 2).

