Change and percentage change from Baseline (Visit T1 (Day 1)) in salivary 17-OHP levels (samples collected on-site) at Visit T2 (Day 29), Visit T3 (Day 57), Visit T4 (Day 85), and Visit T5 (Day 113; Amendment 2) will be evaluated by cohort, nevanimibe dose and overall. For each sampling day, up to five (5) different time points are collected per subject. Summary statistics for each time point will be calculated for each sampling day and used for comparison with data from Visit T1. In addition, for the five (5) on-site salivary samplings, the sum of the h0, h1, h2, h3 and h4 values per subject per study day will be evaluated by cohort, nevanimibe dose and overall, for all subjects with data available at all five timepoints for the respective on-site sampling day. Availability of data for imputation of the missing values will be assessed during the final DRM meeting prior to data analysis, and changes may be made to the described analysis to utilize all available data more effectively. Results will be described using summary statistics for continuous variables.

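### SAP 7.6 sums on-site salivary 17-OHP only in subjects with all of h0 to h4, but on-site saliva is scheduled only at h0, h2 and h4, so no subject qualifies

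*SAP*

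**What the plan says.** **Saliva.** SAP 7.6 summarises on-site salivary 17-OHP at each time point and then adds a daily total: "the sum of the h0, h1, h2, h3 and h4 values per subject per study day will be evaluated". This total is restricted by a completeness rule, being taken only "for all subjects with data available at all five timepoints for the respective on-site sampling day". The same paragraph states that as many as five time points are collected per sampling day. On gaps it says: "Availability of data for imputation of the missing values will be assessed during the final DRM meeting prior to data analysis". It then leaves room to revise the method itself, in that "changes may be made to the described analysis to utilize all available data more effectively".

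The rest of the plan describes three on-site saliva samples:

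- SAP 6.3 defines the endpoint "at time points h0, h2 and h4 (just before, 2 hours after, and 4 hours after (respectively") the morning doses.
- SAP 3.2.1 calculates change from baseline for "salivary 17-OHP values obtained 30 minutes before, as well as 2 hours and 4 hours after intake of the morning dose of nevanimibe HCl".
- SAP 2.3, Table 1 footnote f (amendment 1): "At Visits T1, T2, T3, and T4, saliva samples for 17-OHP will be collected at the study site" at three clock times that stand for predose, 2 hours and 4 hours. Table 2 footnote f (amendment 2) gives the same three times for T1 to T5.
- Protocol 6.11, the visit instructions in Protocol 7.3 and Protocol Appendix 1 footnote f agree.

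**Serum.** Five serum samples (h0 to h4) are scheduled at each treatment visit. SAP 7.6 allows for fewer being available, adds up whatever values the series contains and compares the total with Visit T1. SAP 5.1 uses observed data without imputation unless stated otherwise. The serum paragraph also lists the Follow-up visit, where Protocol 7.4.1 takes a single morning sample.

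**The concern.** A completeness rule that asks for samples nobody is scheduled to give selects nobody. A programmer who follows SAP 7.6 gets an empty salivary sum. Someone must then choose a replacement at data review, in an open-label study where the laboratory results are visible. Protocol 3.3 gives salivary 17-OHP a supporting role in defining efficacy, and SAP Appendix 1 lists a repeated-measurements table for saliva (14.2.2.1), so the output is expected.

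The serum sum has the opposite weakness. It can be computed, but a total over fewer samples is smaller whether or not 17-OHP has changed. Comparing a four-sample total with a five-sample T1 total mixes missing data with treatment effect.

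**Working it through.** **1. Salivary time points, required against scheduled.**

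Required (SAP 7.6): h0, h1, h2, h3, h4. Scheduled (SAP 2.3, 3.2.1, 6.3; Protocol 6.11, 7.3, Appendix 1): h0, h2, h4. Never scheduled on site: h1 and h3.

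| | Visits | Values needed | Values scheduled | Subjects who can qualify |
|---|---|---|---|---|
| Amendment 1 | T1–T4 | 4 × 5 = 20 | 4 × 3 = 12 | 0 at every visit |
| Amendment 2 | T1–T5 | 5 × 5 = 25 | 5 × 3 = 15 | 0 at every visit |

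The plan's count of five on-site saliva time points is therefore not reproduced from its own schedule. The hourly h0 to h4 series is the serum and PK schedule.

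**2. What imputation could supply.** With linear interpolation, h1 = (h0+h2)/2 and h3 = (h2+h4)/2. The five-point sum becomes

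h0 + (h0+h2)/2 + h2 + (h2+h4)/2 + h4 = 1.5·h0 + 2·h2 + 1.5·h4.

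This is a reweighting of the three observed values. It rests on an assumption about the curve and adds no information.

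**3. Serum partial sums (illustration only).** Assume one subject with the same true value c at all five time points and at both visits.

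- One sample missing after T1: 4c/5c − 1 = −20%.
- One sample missing at T1: 5c/4c − 1 = +25%.
- Only the single Follow-up sample, if the sum were applied there: c/5c − 1 = −80%.

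For scale, one subject at −20% moves the mean percentage change by −20/24 = −0.8 to −20/20 = −1.0 points with 20 to 24 subjects. One at +25% moves it by 25/24 = +1.0 to 25/20 = +1.3 points. A flat series is doubtful: h1 to h4 follow the morning glucocorticoid dose, and Protocol 5.7 says its timing may affect 17-OHP. These figures are not bounds. The documents give no rate of missing samples.

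**4. Subjects kept under complete-series rules.** Assume each sample is missing independently with probability p. A rule needing k samples keeps (1 − p)^k of subjects.

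| Rule | k | p = 1% | p = 5% | p = 10% |
|---|---|---|---|---|
| Saliva, three samples on the day | 3 | 97% | 86% | 73% |
| Saliva, three on the day and three at T1 | 6 | 94% | 74% | 53% |
| Serum, five on the day and five at T1 | 10 | 90% | 60% | 35% |

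**The case against.** The best defence is that SAP 7.6 anticipates gaps. It sends imputation and possible changes to the data review meeting, and SAP 2.11 requires changes before final database lock to be written into SAP amendments. That stands as permission to repair the analysis. It is not a rule, and the gap here is two unscheduled time points in every subject, not occasional missing samples.

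Two other readings of the figure five do not rescue the text. It might refer to the five amendment 2 visits, but the sentence names h1 and h3. It might refer to the home saliva profile, which has five samples, but those are taken at clock times through the day and the sentence is about on-site sampling.

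A reader might infer more than the documents support:

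- *That h1 and h3 cannot be imputed.* They can be interpolated, as shown above. The fair criticism is that no method is stated and nothing is gained.
- *That the rule will be set after Cohort 1 results are known.* SAP 5.4 plans a review meeting for each cohort, and SAP 2.10 allows Cohort 1 to be analysed first. But SAP 7.6 places the final meeting before data analysis. The sequence is possible but is conjecture.
- *That the serum sum has no missing-data rule.* SAP 5.1 read with SAP 7.6 points to summing the observed values. The objection is to what that rule does. The T1 comparator is also largely given, in SAP 6.3 and 7.6.

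**Conclusion.** The salivary sum is wrong as written: from scheduled samples it has no eligible subjects at any visit under either amendment. This follows from the documents alone and needs no assumption.

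The serum point holds in smaller form. Summing observed values lets a missing sample appear as a change in 17-OHP. The size depends on the shape of the series and on how often samples are missing. The first is assumed here and the second is unknown, so the net effect cannot be stated.

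Severity is minor. SAP 7 makes all summaries exploratory, and these are secondary ones. It would be a mistake to infer that collected data are lost or that the efficacy conclusion is at risk. The salivary summaries at h0, h2 and h4 work as written, and the primary endpoint uses predose serum 17-OHP only.

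**What to change.** Amend the SAP by the route in SAP 2.11, before the first cohort analysis.

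1. **Saliva.** Define the on-site sum as h0+h2+h4 in subjects with all three samples on that sampling day. Compare it with the T1 h0+h2+h4 sum where that is complete. Correct the number of on-site time points in SAP 7.6 from five to three. Say in SAP 3.2.1 that this comparison uses the T1 series, because the salivary predose baseline there may otherwise be averaged with an earlier value.
2. **Serum.** Compare each visit with T1 over the same time points only, using either complete series at both or the mean over time points present at both. Limit the serial sum to T1–T5, and compare Follow-up as a predose value against the predose baseline.
3. **Clerical.** In the serum paragraph of SAP 7.6, correct the labels to T2 (Day 29), T3 (Day 57) and T4 (Day 85).

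The cost is wording and programming; no new samples are needed. The downside is that subjects with incomplete series drop out of the sums, to the extent tabulated above. For serum, the mean over shared time points keeps more subjects, but it is less precise and is less comparable between subjects if the percentage change differs across time points.

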7.7 Evaluation of Safety Endpoints

All safety variables will be evaluated for the safety population (SP). The analyses of treatment-emergent adverse events (TEAEs) will be performed overall and for subjects enrolled under global

amendment 1 and global amendment 2 separately. The analysis on the SOC and PT level will be repeated for the All Screened population to cover all AEs, also those recorded prior to first treatment with the study drug.

Treatment-emergent adverse events (TEAEs) will be summarized overall and by causal relationship and severity. TEAEs will be coded using the latest MedDRA version at the time of database close. Incidences and percentages will be provided on the subject-level (n), overall as well as on the system organ class (SOC) level and on the preferred term (PT) level for all subjects and by nevanimibe dose category. Results will additionally be prepared by time range. The suitable time ranges will be selected during the DRM for Cohort 1. A subject with more than one AE overall or assigned to one SOC or assigned to one PT will be counted once for the worst category (causal relationship or severity) on the subject level. For the summarization by relationship to study drug, the relationship will be categorized as “related” and “not related,” where related AEs are those with at least a possible relationship to the study treatment. For the summarization by nevanimibe dose, subjects with more than one AE overall or assigned to one SOC or assigned to one PT will be counted once on the subject level at the lowest nevanimibe dose category on which they experience the AE (i.e., a subject with two AEs, one when treated with 1000 mg BID and one when treated with 1500 mg BID, will be counted once at the 1000 mg BID dose). Additionally, the number of AEs per patient-year of treatment will be calculated by nevanimibe dose as (sum of number of AEs of subjects at the respective nevanimibe dose) / (patient-years of treatment at the respective nevanimibe dose).

The mean time to onset of AEs (including worsening of preexisting conditions) will additionally be presented using summary statistics for continuous variables, overall and by SOC and PT. Time to first treatment-related TEAE and/or onset of selected TEAEs/groups of TEAE, may further be displayed in a Kaplan-Meier curve(s), by dose and/or in total, and by cohort and in total, where the time reflects the number of days since first being treated with the corresponding dose and changes to the dose will be included as censored information. If a subject is treated at a certain dose, then the dose is changed and at a later point, the subject is treated with the same dose again, then the duration of treatment with said dose will be added to the initial treatment period. Serious adverse events (SAEs) as well as AEs leading to death or discontinuation will be listed. Additionally, SAEs will be summarized overall and by nevanimibe dose.

Laboratory assessments, physical examinations, ECG and vital signs will be evaluated as continuous or categorical variables according to standard summary statistics for each visit, overall. Changes from baseline will be calculated for continuous variables and shift tables depicting the change from baseline will be produced for categorical variables where applicable and meaningful.

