9.6.2. Safety Analyses

No inferential statistical analyses will be performed on the safety data from this study. The Safety Population will be used for all summaries of safety data. Only observed case data will be used. The summarization of AEs will include treatment-emergent AEs (TEAEs; defined as AEs that begin or worsen after the first dose of study drug). TEAEs and treatment-emergent SAEs (TESAEs) will be summarized by MedDRA system organ class (SOC) and preferred term (PT), severity, and relationship to study drug, overall, by nevanimibe HCl dose, and by cohort. Deaths and discontinuations due to AEs will each be summarized, overall, by nevanimibe HCl dose, and by cohort. Clinical safety laboratory results, PE findings, vital signs, and ECG readings will be summarized by value and by change from baseline in the value, where appropriate, for each time point, overall, by nevanimibe HCl dose, and by cohort using summary statistics for continuous parameters, including number of non-missing observations (n), mean and/or median, standard deviation (SD) and/or percentiles, minimum (min), and maximum (max). Frequencies and percentages as well as shift tables will be prepared for categorical parameters.

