4.2 Subgroups

Two cohorts (Cohort 1 and Cohort 2) are included in this trial. Eligible subjects are assigned to Cohort 1 if their serum 17-OHP is $\geq 4x$ ULN at the initial screening visit. If this is not the case, subjects may undergo a reduction in glucocorticoid dose and will be reassessed for their serum 17-OHP value. If the serum 17-OHP level is $\geq 4x$ ULN after reassessment, the subject can be enrolled into Cohort 2. No formal group sizes have been appointed for Cohort 1 and 2. All efficacy and PK analyses will be performed overall and by cohort.

Additionally, levels of androstenedione, testosterone and 11-ketotestosterone will be summarized by sex (male, female).

To assess the possible impact of protocol amendment 2 on the safety profile, the analysis of adverse events will be repeated for the subgroup of subjects enrolled according to global amendment 1 and global amendment 2.

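### SAP 7.7 omits the by-cohort safety summaries and the by-dose laboratory, examination, vital-sign and ECG summaries that protocol 9.6.2 requires, and SAP section 8 does not declare the difference

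*SAP*

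**What the plan says.** Protocol 9.6.2 sets the same three splits for all its safety summaries:

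- For treatment-emergent AEs and SAEs, tabulated by SOC and PT, the further breakdown is "severity, and relationship to study drug, overall, by nevanimibe HCl dose, and by cohort".
- Fatal events and AE withdrawals get their own sentence: "Deaths and discontinuations due to AEs will each be summarized, overall, by nevanimibe HCl dose, and by cohort".
- Laboratory, physical examination (PE), vital-sign and ECG results are summarized "for each time point, overall, by nevanimibe HCl dose, and by cohort using summary statistics for continuous parameters".

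SAP 7.7 specifies less:

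- Treatment-emergent AEs are tabulated "on the preferred term (PT) level for all subjects and by nevanimibe dose category", with separate runs for subjects enrolled under each protocol amendment.
- For serious events, fatal events and AE withdrawals, the commitment is a listing: "Serious adverse events (SAEs) as well as AEs leading to death or discontinuation will be listed". Only the serious events also get a summary: "Additionally, SAEs will be summarized overall and by nevanimibe dose".
- Laboratory, PE, ECG and vital signs are evaluated "according to standard summary statistics for each visit, overall".

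Cohort appears in SAP 7.7 only for Kaplan-Meier curves, which are optional. SAP 4.2 states that "All efficacy and PK analyses will be performed overall and by cohort"; for safety it adds a repeat of the AE analysis by amendment. SAP section 8, which lists changes from the protocol, names only the redefinition of the per-protocol population.

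**The concern.** Safety is half of the primary objective, and SAP 2.5 asks whether the higher doses used here still have an acceptable safety profile. Followed as written, SAP 7.7 would not show laboratory, PE, vital-sign or ECG results by dose.

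The two cohorts also differ in steroid background. Under protocol 3.1.1, Cohort 1 keeps its maintenance glucocorticoid dose, while Cohort 2 is treated after a planned reduction. The brief examinations look specifically for adrenal insufficiency (protocol 6.8), so this background bears on how safety data are read. The protocol calls for the cohorts to be shown separately. SAP 7.7 does not require it and gives no reason.

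**Working it through.** **1. Requirement against specification**

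| Output | Protocol 9.6.2 | SAP 7.7 | Not specified in 7.7 |
|---|---|---|---|
| Treatment-emergent AEs | overall, dose, cohort | overall, amendment, dose | cohort |
| SAEs | overall, dose, cohort | overall, dose | cohort |
| Deaths | overall, dose, cohort | listed; also within the SAE summaries, since death is an SAE criterion (protocol 6.10.4.1) | a separate count; cohort |
| AE discontinuations | overall, dose, cohort | listed | a summary under any split |
| Laboratory, PE, vital signs, ECG | per time point: overall, dose, cohort | per visit, overall | dose, cohort |

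**2. Whether visit stands in for dose**

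Inputs are the starting doses and titration steps in SAP 2.2. The dose shown is the one taken just before the visit, for a subject who has not met the 17-OHP target and has had no safety reduction.

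| Visit day | Amendment 1 (mg BID) | Amendment 2 (mg BID) | Ratio |
|---|---|---|---|
| 29 | 1000 | 500 | 1000/500 = 2.0 |
| 57 | 1500 | 1000 | 1500/1000 = 1.5 |
| 85 | 2000 | 1500 | 2000/1500 = 1.33 |

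At Day 29 this holds for every subject without a safety reduction, because no response-based titration has yet happened. At Days 57 and 85 it holds only for those still up-titrating.

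The gap is 500 mg BID at each visit. If a share p of these subjects is under Amendment 1, the mean preceding dose at Day 29 is 500 + 500p. Neither document gives p. Assuming p = 0.10, 0.25 or 0.50 gives 550, 625 or 750 mg BID. At p = 0 or p = 1 there is no mixing by amendment.

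Mixing by response remains within an amendment. Under Amendment 2, a subject who met the target at Day 29 reaches Day 57 on 500 mg BID and one who did not reaches it on 1000 (protocol 3.1.3).

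**3. Which data this touches**

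From the schedules in SAP 2.3, hematology, chemistry, ACTH and cortisol, vital signs and PE are collected at each of these visits, so the table in step 2 applies to them.

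ECG, coagulation and post-baseline urinalysis are scheduled on treatment only at end of treatment: Day 85 under Amendment 1 and Day 113 under Amendment 2. A subject who up-titrates throughout is then on 2000 mg BID under either amendment (2000/2000 = 1.0), so the ratios above do not apply. End-of-treatment doses can still differ through response or a safety reduction.

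**4. What pooling the cohorts can hide**

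SAP 2.9 sets no cohort sizes, so the sizes here are assumptions. An AE seen in 6 of 20 subjects (30%) is compatible with each of these:

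- 10 + 10 subjects: 3/10 and 3/10, or 0/10 and 6/10
- 14 + 6 subjects: 4/14 and 2/6, or 0/14 and 6/6
- 16 + 4 subjects: 5/16 and 1/4, or 2/16 and 4/4

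This shows what a pooled column cannot distinguish. It does not predict a difference.

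**The case against.** The strongest defence is the opening of SAP section 7, which provides for analyses by cohort, by dose or visit, and overall. It governs 7.7. But it applies only where the split is judged to make sense, and it joins dose and visit with *or*, whereas the protocol wants time point and dose. SAP 7.7 then names its own splits. The preamble makes this an unclear omission rather than an explicit reversal; it does not clearly restore the splits.

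Table content may also supply some of what is missing. Appendix 1 says its titles are not binding and refers layout to mock tables that are not part of these documents. The by-cohort disposition table may show AE withdrawals, and the AE overview table may count deaths or discontinuations by dose. These are possibilities, not commitments.

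It is also fair that safety is descriptive, with no inferential analysis and no targets, and that subject-level AE and laboratory listings are planned. That limits the consequence and stands.

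A reader might infer four stronger things that the documents do not support:

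- **That SAP 4.2 rules out by-cohort safety work.** It is not an exhaustive list: demographics, baseline characteristics, exposure and disposition are by cohort without being named there.
- **That deaths would go uncounted.** Fatal AEs are SAEs, and SAEs are summarized overall and by dose.
- **That the cross-amendment ratios apply to ECG.** The visit schedule excludes this.
- **That the study report would hide the departure.** SAP 2.11 says deviations will be summarized in the report. Only the absence from section 8 can be shown.

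**Conclusion.** The mismatch is real and should be corrected, but its consequence is modest. SAP 7.7 requires no by-cohort AE or SAE summary and no summary of AE discontinuations. It gives laboratory, PE, vital-sign and ECG results neither by dose nor by cohort. Section 8 is silent on all of this.

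For the assessments made at every treatment visit, a visit-only table can combine preceding doses that differ by 500 mg BID between amendments, a ratio of 2.0 at Day 29 falling to 1.33 at Day 85. This rests on subjects following the planned up-titration and on both amendments contributing subjects; how much mixing results cannot be computed without the Amendment 1 share. For ECG, coagulation and urinalysis the point is only that the dose and cohort splits required by the protocol are not specified.

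No inference, success criterion or stopping rule changes.

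**What to change.** In SAP 7.7:

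1. Add cohort columns to the treatment-emergent AE and SAE summaries.
2. Add summary counts of deaths and AE discontinuations overall, by dose and by cohort, alongside the listings.
3. Add dose and cohort splits to the laboratory, PE, vital-sign and ECG summaries. Use the dose categories of SAP 7.10 and assign each visit value to the dose taken just before that visit.
4. Declare and justify in section 8 any of these splits that will not be produced.

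The cost is SAP wording and extra table columns from data already collected. The downside is small counts. With the illustrative cohort sizes above, exact (Clopper-Pearson) 90% intervals run from 8.7% to 60.7% for 3/10, 6.3% to 72.9% for 2/6 and 1.3% to 75.1% for 1/4. The columns would describe the cohorts and could not establish a difference between them. If that is thought reason enough to drop a split, section 8 is the place to say so.
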